9.4.2 ANALYSIS OF THE SECONDARY ENDPOINT(S)

We will explore heterogeneity of treatment effects by using Model 2 to assess whether receptivity to study arm (e.g., personal messaging/loss protection) differs by significant social determinants of health identified in Hypotheses 1 through 5. To assess seroprevalence trends, we will use separate hierarchical models with a random household intercept to regress seropositivity status (yes vs. no), IgG value, and IgM value on testing time (Time 1 vs. Time 2).

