3 OBJECTIVES AND ENDPOINTS

OBJECTIVES	ENDPOINTS	JUSTIFICATION FOR ENDPOINTS
Primary		
To evaluate the effectiveness of risk-based messaging and incentives that promote repeated testing for SARS-CoV-2 antibodies	Main effect of incentives, the main effect of messaging strategy, and the interactions between incentives and messaging and covariates; seropositive status	We have found that providing at-risk incentives that can be insured with repeat health behavior outperforms direct cash payments of the same expected value.
Secondary		
To understand social and behavioral determinants of COVID-19 testing and variations within sub-groups of this population.	Characterize barriers to access, bias, risk attitude and incentive preferences through outreach and survey responses. Identify groups that may partition facilitators to testing into minimal and maximal effectiveness.	covariates

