4.1 OVERALL DESIGN

Social determinants need to be understood in the context of actionable facilitators (things COVID-19 policymakers can do) to encourage repeat testing. We will study two types of facilitators (messaging and financial incentives) and evaluate the heterogeneity of treatment response based on the characteristics of those tested. We will conduct a 2 x 2 (messaging x financial incentive) factorial design (Aim 3) that stratifies on social and behavioral determinants (Aim 2) collected as part of an initial survey (Aim 1). We have been studying ways to identify powerful incentives for repeated health behaviors. We have found that providing at-risk incentives that can be insured with repeat health behavior outperforms direct cash payments of the same expected value. Individuals were 70% more likely to return to a health screening when insuring against losing a baseline incentive than they were when paid cash ($p < 0.01$).⁴ In addition, in a recent study we showed that disadvantaged patients at a federally-qualified health center were more likely to repeat a health behavior twice each week over 12 weeks when repetition

was insuring against losing a weekly incentive than if they were paid equivalently in cash (see Figure 1; $p < 0.05$).

5

Figure 1. Insurance (loss protection) vs. cash (control) incentive for repeat health behavior among disadvantaged persons (N = 151)

2 x 2 Stratified Randomization

Messaging (Factor 1): We will develop simple messaging that frames the decision to test in terms of either: (i) family risk, or, (ii) personal risk. These methods will be piloted, but will be of the form "Antibody testing will help you understand your family's risk of getting COVID-19"; and, "Antibody testing will help you understand your risk of getting COVID-19". Family risk framing may engender concern for loved ones. It may also make it easier to mentally simulate family burdens with COVID-19 such as knowing how several people in the family becoming sick could adversely affect the lives of everyone in the family. We hypothesize that the family framing will result in greater uptake of testing and greater repeat testing.

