9.4 STATISTICAL ANALYSES

9.4.1 GENERAL APPROACH

Aim 1 (Hypotheses 1-5): Data from the baseline survey combined with data on which heads of households attended Time 1 testing will be used to address Aim 1. In particular, we will estimate logistic regressions where the dependent variable will be the binary indicator whether the head of household attended Time 1 testing (yes vs. no). The key independent variables will include: 1) prior COVID-19 testing, 2) which SARS-CoV-2 information sources are most trusted, 3) risk aversion, 4) heads of households or family member diagnosis of a health condition (e.g., diabetes, hypertension) and, 5) race/ethnicity, income, discriminatory incidences, household receipt of Supplemental Nutrition Assistance Program (SNAP) or Supplemental Security Income (SSI) benefits, and citing money as the biggest vaccine barrier.

$$\pi = \beta_0 + \beta_1 x_i + \varepsilon_i \quad [1]$$

$\pi = \ln\left(\frac{p}{1-p_i}\right)$; p_i , is the probability of attending Time 1 testing, by head of household i , and β_1 is each head of household reported social determinant of health. This will allow us to identify significant social and behavioral determinants for heterogeneity of effects (currently hypothesized in Hypotheses 1-5 above).

Aim 2 (Hypotheses 1r-4r): Aim 2 will involve regressing Time 2 retesting (yes vs. no) on the following items for Hypotheses 1r-4r: 1r) risk aversion, essential worker status, access to personal protective equipment, and risky forms of transportation (e.g., personal vehicle, carpool, bus), 2r) income, discriminatory incidences, employment status, whether heads of households personally, or other family members suffer from depression and/or mental health issues, and household receipt of Supplemental Nutrition Assistance Program (SNAP) or Supplemental Security Income (SSI) benefits, 3r) Time 1 seropositivity status and, 4r) the Financial Incentive and Messaging study arms.

$$\pi = \beta_0 + \beta_1 x_i + \beta_2 x_i + \beta_3 x_i + \varepsilon_i \quad [2]$$

For Hypotheses 1r-2r, $\pi = \ln\left(\frac{p}{1-p_i}\right)$, is the probability of Time 2 attendance by head of household i given they attended Time 1 testing; β_1 is the main effect of the head of household reported characteristic, β_2 is the main effect of the Financial Incentive, where the lottery condition is the reference, and β_3 is the interaction between the head of household reported social determinant of health and Financial Incentive.

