$$\pi = \beta_0 + \beta_1 x_{ij} + \eta_j + \varepsilon_i \quad [3]$$

For Hypothesis 3r, we will use a simple mixed-effects logistic model, where $\pi = \ln\left(\frac{p}{1-p_i}\right)$, is the probability of Time 2 attendance by individual i in household j given they attended Time 1 testing; β_1 is seropositivity status at Time 1 (yes vs. no); and η_j is the random intercept for each household capturing household-level effects.

We will use two separate models for Hypothesis 4r.

$$\pi = \beta_0 + \beta_1 x_{ij} + \beta_2 x_{ij} + \beta_3 x_{ij} + \beta_4 x_{ij} + \beta_5 x_{ij} + \eta_j + \varepsilon_i \quad [4a]$$

Model 4a will assess the probability, $\pi = \ln\left(\frac{p}{1-p_i}\right)$, of testing attendance for individual i in household j , where β_1 is the main effect for testing time (reference = Time 1); β_2 is the main effect for Financial Incentives (reference = lottery condition); β_3 is the main effect for Messaging (reference = personal); β_4 is the interaction between testing time and Financial Incentives; β_5 is the interaction between testing time and Messaging; and η_j is the random intercept for each household.

$$\pi = \beta_0 + \beta_1 x_{ij} + \beta_2 x_{ij} + \beta_3 x_{ij} + \beta_4 x_{ij} + \beta_5 x_{ij} + \beta_6 x_{ij} + \beta_7 x_{ij} + \eta_j + \varepsilon_i \quad [4b]$$

Model 4b will assess the probability, $\pi = \ln\left(\frac{p}{1-p_i}\right)$, of testing attendance for individual i in household j , where β_1 is the main effect for testing time (reference = Time 1); β_2 through β_4 are the main effects for study arm (personal messaging and loss protection, family messaging and lottery, family messaging and loss protection), where personal messaging and lottery is the reference group; β_5 through β_7 are the interactions between study arm and testing time; and η_j is the random intercept for each household.

For Models 4a and 4b, we will use unrestricted random sampling to select 3,000 observations, 2,000 times, clustered by household to bootstrap 95% confidence intervals for probability differences. We

will test differences in effect sizes for Model 4a (β_4 vs. β_5) and 4b (β_5 vs. β_6 ; β_5 vs. β_7 ; β_6 vs. β_7) using equality of regression coefficients tests.⁶ We will also calculate the inverse of observed probabilities to derive the Number Needed to Intervene on (NNI), and calculate standard errors by taking the square root of $P * (1 - P)/N$.⁷

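### Section 9.4.2 assigns Model 2 to study-arm heterogeneity, but Model 2 has no messaging term and no other written model supplies a messaging-by-characteristic term

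*Combined protocol and SAP*

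**What the plan says.** Section numbers are those in the body of the document.

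- **Section 9.4.2 (secondary endpoints)** sets out an exploratory look at how treatment response varies, "using Model 2 to assess whether receptivity to study arm (e.g., personal messaging/loss protection) differs by significant social determinants of health". The determinants are those found significant under Hypotheses 1 to 5. The example arm is defined jointly by a message and an incentive.
- **Section 9.4.1 (Model 2)** defines each coefficient for Hypotheses 1r and 2r. The first is the characteristic reported by the head of household. The second "is the main effect of the Financial Incentive, where the lottery condition is the reference". The third "is the interaction between the head of household reported social determinant of health and Financial Incentive". The outcome "is the probability of Time 2 attendance by head of household", among those who attended Time 1.
- **Section 4.1** names messaging and financial incentives as the two facilitators to be studied and says the trial will "evaluate the heterogeneity of treatment response based on the characteristics of those tested".
- **Section 3** lists, in the primary-objective row, "the interactions between incentives and messaging and covariates".
- **Section 1.1** places the interventions' heterogeneous treatment effects among the secondary endpoints.

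**The concern.** The target in 9.4.2 is response to study arm, and an arm in this trial is a message combined with an incentive. The model assigned to that target knows only the incentive. It pools personal messaging with loss protection and family messaging with loss protection into one group, so it cannot isolate the arm that 9.4.2 gives as its example. It also has no coefficient for whether the effect of family versus personal framing depends on a characteristic.

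An analyst who follows the text would report heterogeneity for one facilitator out of two. An analyst who wants to honour the stated aim would have to devise the missing terms, coding and reference group, possibly after seeing the data and across many determinants.

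**Working it through.** The plan gives no figure for this point. The check compares model terms with the stated use, and then counts parameters.

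**1. What each written model contains (section 9.4.1)**

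| Model | Treatment terms | Treatment interacted with | Messaging x characteristic? |
|---|---|---|---|
| 1 | none | – | no |
| 2 | incentive | characteristic | no |
| 3 | none (Time 1 serostatus only) | – | no |
| 4a | incentive, messaging | testing time | no |
| 4b | three arm indicators | testing time | no |

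In Model 4a the only interaction that involves messaging "is the interaction between testing time and Messaging". In Model 4b the interaction terms "are the interactions between study arm and testing time". Neither model includes a social determinant. Section 9.4.6 promises analyses by sex/gender and race/ethnicity but writes no model, and section 9.4.8 plans no exploratory analyses.

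**2. Can the design support the missing term?**

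Let X be a characteristic with k categories (k − 1 indicators), F the incentive and M the messaging.

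- Model 2 (1, X, F, XF): 1 + (k − 1) + 1 + (k − 1) = 2k parameters.
- Factor-level model (1, X, F, M, XF, XM): 1 + (k − 1) + 2 + 2(k − 1) = 3k parameters.
- Four-arm model (1, X, three arms, three arms x X): 1 + (k − 1) + 3 + 3(k − 1) = 4k parameters.

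For a binary X (k = 2) these give 4, 6 and 8. A design matrix with 135 households per cell (540/4) and a binary X had rank 4, 6 and 8, so all three models are of full rank. The crossed factors supply the information; Model 2 leaves it out.

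**3. Precision**

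Assume equal allocation over the four cells and similar outcome variance v in each, with N heads of household analysed.

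- Factor contrast, N/2 against N/2: variance = v(2/N + 2/N) = 4v/N.
- Arm contrast, N/4 against N/4: variance = v(4/N + 4/N) = 8v/N.
- Ratio of standard errors = √(8/4) = √2 ≈ 1.41, about 40% larger.

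The same ratio holds within each level of X, and so for the interaction with X.

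**4. Illustration only**

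A simulation of 1,000 replicates used assumptions that are not in the documents: 540 households all analysed, binary X at 50%, and log-odds = 0.4F + 0.4M + 0.8MX. Model 2's one interaction (XF) was significant at 5% in 5.5% of replicates, about the nominal rate. The XM term in the factor-level model was significant in 57.8%. The first result follows by construction, since Model 2 has no term for the effect. The second depends wholly on the assumed 0.8 and is not a power claim for this trial.

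**The case against.** The best counter-argument is that 9.4.2 borrows only the form of Model 2. Equation [2] is generic, and the incentive definition is introduced specifically for Hypotheses 1r and 2r. Section 9.4.2 already changes one input, taking its determinants from Hypotheses 1 to 5, and the arm it names is one of the levels coded in Model 4b. On that reading study arm replaces the incentive and messaging is included. This is plausible, but the text does not state it. It also leaves open whether to use a messaging term or three arm indicators, and against which reference. The only reference given for Model 2 is the lottery condition.

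Three stronger inferences are tempting, and the documents do not support them.

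- A reader might infer that the trial cannot estimate heterogeneity in response to messaging. It can: both extended models are of full rank.
- A reader might infer that half of the pre-specified heterogeneity question is lost. The hypotheses that section 9.1 identifies as heterogeneity hypotheses, 1r and 2r, concern incentives only, and Model 2 fits them. The messaging part is exploratory.
- A reader might infer that the main comparison of the arms is compromised. Hypothesis 4r uses Models 4a and 4b, which contain messaging and are unaffected.

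**Conclusion.** The mismatch is real and minor. As written, the model assigned in 9.4.2 does not address the target set there, and none of the five written models has a messaging-by-characteristic coefficient. Of the two factor-by-characteristic interactions that the aim in section 4.1 implies, the plan specifies one. Section 3 is loosely worded, but its natural reading also covers messaging by covariates, so the gap touches that row of the endpoint table as well.

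The conclusion rests on the coefficient definitions in 9.4.1 and on no numerical assumption. The parameter counts assume one characteristic per model. The figure of about 40% assumes equal allocation and similar outcome variance across arms.

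**What to change.** Leave Model 2 unchanged for Hypotheses 1r and 2r, so that their analysis is not altered. In 9.4.2, replace the reference to Model 2 with a separate heterogeneity model:

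logit(p) = β0 + β1·characteristic + β2·incentive + β3·messaging + β4·(characteristic x incentive) + β5·(characteristic x messaging)

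State the references (lottery; personal messaging, as in Model 4a) and report β4 and β5 with confidence intervals for each determinant. If arm-level receptivity is wanted, add as a supportive analysis the Model 4b arm coding (reference personal messaging and lottery) interacted with the characteristic.

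**Cost.** This is a text change, with no new data, visits or participants. The factor-level model adds two terms to the Model 2 form for a binary or linear determinant, with little loss of precision. A determinant with k categories adds k terms. The four-arm version adds four terms for a binary determinant (2k in general), and its arm contrasts carry the larger standard errors shown above, which is why it is better kept as supportive.

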9.1 STATISTICAL HYPOTHESES

The figure below provides a conceptual diagram for thinking about what factors may influence testing take-up and retesting. Testing take-up would depend on several factors, including prior beliefs about infection, health literacy, information networks, health conditions, demographics and socio-economics. We have the following hypothesis based on analysis of literature on testing for HIV and Hepatitis as well as preliminary analysis of data from our prior study:

Hypothesis 1: Those who believe that they have been infected in the past would be more likely agree to testing to confirm that they have antibodies and potential immunity; **Hypothesis 2:** People with poor health literacy will be less likely to agree to testing as they might find it daunting to understand what the test does and how to interpret results; **Hypothesis 3:** Those who are risk averse would be more likely to agree to testing as it reduces uncertainty about serostatus; **Hypothesis 4:** Those with preexisting health conditions would be more likely to agree to testing as they face higher risks from COVID-19 and thus have more to gain from learning serostatus; **Hypothesis 5:** Minorities and those in lower socio-

economic strata would be less likely to agree to testing due to fear of discrimination, lack of trust in health care/research, poor past experience, and perception of being at low risk of infection. We also generate hypotheses for facilitators to retesting (r) relative to those who take a first test **Hypothesis 1r:** Persons who practice low COVID-19 mitigation, exhibit risk-seeking and have high exposure risk may respond to a lottery retest incentive. **Hypothesis 2r:** Those persons with low income, unemployed, or have high stress or anxiety may respond most to insurance of incentives. **Hypothesis 3r:** Persons who are sero+ at baseline will be less likely to return for a retest. **Hypothesis 4r:** Lottery insurance and family messaging will induce higher retesting rates. Hypotheses 1-5 are covariates that may affect agreeing to the test. Hypotheses 1r and 2r refer to heterogeneity of treatment effects for retesting, while 3r and 4r are main effects on retesting.

Conceptual diagram

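### Section 9.4.2 admits characteristics to the study-arm heterogeneity analysis only if they predict first-test attendance, so some modifiers of the incentive effect and all listed modifiers of messaging face an unrelated filter

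*Combined protocol and SAP*

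**What the plan says.** Section 3 lists this among the secondary endpoints: "Identify groups that may partition facilitators to testing into minimal and maximal effectiveness".

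Section 9.4.1, Aim 1, fits logistic Model 1, in which "the dependent variable will be the binary indicator whether the head of household attended Time 1 testing (yes vs. no". Nine determinants are listed as predictors: prior COVID-19 testing, trusted information sources, risk aversion, health conditions, race/ethnicity, income, discriminatory incidences, SNAP/SSI receipt, and money as the main vaccine barrier. The section then gives the model a second purpose: "This will allow us to identify significant social and behavioral determinants for heterogeneity of effects".

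Section 9.4.2 takes up that purpose. Its aim, with Model 2 as the tool, is to "assess whether receptivity to study arm (e.g., personal messaging/loss protection") varies across participants. The characteristics considered are restricted, since the stated question is whether response "differs by significant social determinants of health identified in Hypotheses 1 through 5".

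A separate route exists. Section 9.1 states that "Hypotheses 1r and 2r refer to heterogeneity of treatment effects for retesting". Section 9.4.1, Aim 2, gives these hypotheses their own item lists, beginning "1r) risk aversion, essential worker status, access to personal protective equipment, and risky forms of transportation" and "2r) income, discriminatory incidences, employment status"; the second list goes on to mental health and SNAP/SSI. Each item enters Model 2 with an interaction with the financial incentive, and Model 1 significance is not a condition. As written, Model 2 contains no messaging term.

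**The concern.** The screen and the question it serves differ in three ways. The outcome of Model 1 is first-test attendance, whereas Model 2 concerns retesting. The population of Model 1 is surveyed heads of household, whereas Model 2 is restricted to those who attended Time 1. Model 1 estimates a main effect with no arm term, whereas Section 9.4.2 needs an arm-by-characteristic interaction. A null main effect on attendance does not imply a null interaction on retesting.

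Section 6.1.2 adds a further problem. Participants hear about their arm during the recruitment call, before Time 1. A trait that raises attendance in one arm and lowers it in another can average to nothing in Model 1 and be discarded. That crossover is a pattern that an analysis of which facilitator suits whom should be able to find.

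The secondary endpoint on least and most responsive groups is at stake. A report of no heterogeneity would partly reflect characteristics that were never examined.

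**Working it through.** The plan states no figure for this selection rule, so there is nothing to reproduce. The check has two parts: which characteristics are exposed, and how often the screen removes a real modifier.

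**1. Exposure.** The nine Model 1 determinants, set against the unscreened 1r/2r lists in Section 9.4.1:

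| Determinant | Incentive interaction tested without a screen? | Messaging or combined-arm interaction tested without a screen? |
|---|---|---|
| Risk aversion | Yes (1r) | No |
| Income | Yes (2r) | No |
| Discriminatory incidences | Yes (2r) | No |
| SNAP/SSI receipt | Yes (2r) | No |
| Prior COVID-19 testing | No | No |
| Trusted information sources | No | No |
| Health conditions | No | No |
| Money as vaccine barrier | No | No |
| Race/ethnicity | No* | No* |

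*Section 9.4.6 promises to look at differences by race/ethnicity but names no model or interaction.

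So (a) five determinants are exposed for any arm, and (b) all nine are exposed for messaging and the combined arms.

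**2. Chance of passing the screen.** Assumptions: two-sided 5% (no level is stated), a binary characteristic split 50:50, and 50% uptake. The number of surveyed heads runs from 540 (the households in Section 9.2) to 1000 (the households sampled in Section 5), giving n = 270 or 500 per group.

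For an uptake difference d, p1 = 0.5 − d/2 and p2 = 0.5 + d/2.
SE = √[(p1(1−p1) + p2(1−p2))/n]; P(pass) ≈ Φ(d/SE − 1.96) + Φ(−d/SE − 1.96).

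| d | n = 270 per group | n = 500 per group |
|---|---|---|
| 0 | 5% | 5% |
| 5 points | SE 0.0430, d/SE 1.16: 21% | SE 0.0316, d/SE 1.58: 35% |
| 10 points | SE 0.0428, d/SE 2.34: 65% | SE 0.0315, d/SE 3.18: 89% |

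The first row is the assumed level itself and does not depend on n or uptake. A modifier unrelated to uptake is dropped with probability 1 − α: 95% at α = 0.05, 90% at 0.10, 99% at 0.01.

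**3. Detection with and without the screen.** A simulation (10,000 runs per setting) assumed 1000 surveyed heads, 54% attending (540), a 50:50 trait unrelated to uptake, 50% retesting in the reference arm, and 5% tests at both steps.

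| Arm effect in the two trait groups | No screen | With screen |
|---|---|---|
| 0 v 20 points | 67% | 3.5% |
| 0 v 30 points | 97% | 4.8% |

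**4. Power after a multiplicity correction.** For a two-level factor, 540 attenders give 540/4 = 135 per trait-by-arm cell. With three cells at 50% and one at 70%:
SE = √[(3 × 0.25 + 0.70 × 0.30)/135] = 0.0843; 0.20/0.0843 = 2.37.
- At 0.05: Φ(2.37 − 1.96) = 66%.
- At 0.05/9 (critical value 2.77): Φ(2.37 − 2.77) = 34%.

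The level 0.05/9 is roughly the false discovery rate threshold when one of nine items is a true modifier.

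Cells shrink to 67.5 if only 270 heads attend (540 surveyed at 50%), or if two of the four combined arms are compared among 540 attenders (270/4). Then SE = 0.1193 and 0.20/SE = 1.68. Power is 39% at 0.05 and 14% at 0.05/9, and detection under the screen is about 0.05 × 39% = 2%.

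**The case against.** A reader might infer that every characteristic which changes response without affecting uptake goes untested. The documents do not support that. Risk aversion, income, discriminatory incidences and SNAP/SSI are tested against the incentive whatever Model 1 shows, as are essential work, protective equipment, transportation, employment and mental health.

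A reader might also count chance entry as a harm: with ten independent null items, 1 − 0.95^10 = 40% would see at least one pass. That carries little weight. Items such as income and SNAP/SSI are unlikely to be independent, and an item that passes by chance only receives an interaction test, which it should receive anyway.

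The strongest defence is that the analysis is worded as exploration, and that asking whether the arms work in groups that under-test is a legitimate question. It fits Section 9.2, which forms subgroups from predictors of participation, and the emphasis in Section 2.2 on low-uptake groups. This stands as a reason to examine those predictors. It does not justify excluding the rest, because the endpoint in Section 3 asks where the facilitators work least and most, whether or not those groups under-test. Exploratory wording does not make an unexamined item a negative finding.

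One could read the word significant in Section 9.4.2 loosely, as important. Section 9.4.1 ties it to the Model 1 regressions.

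**Conclusion.** The concern holds for the study-arm analysis in Section 9.4.2. This is a stated rule that selects on the wrong quantity, not a missing detail. It affects the five determinants in (a) for any arm and all nine for messaging and the combined arms. It does not affect the incentive interactions under Hypotheses 1r and 2r.

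The loss of about 95% of modifiers unrelated to uptake depends only on the assumed 5% screen. The 21–35% and 65–89% pass rates also depend on the number surveyed, 50% uptake and an even split; a larger survey would raise them. Detection of roughly 3–5% under the screen assumes 540 attenders and a 50% reference retest rate, and is lower with fewer attenders. The point concerns an exploratory secondary analysis that is partly covered elsewhere, so it should be corrected but does not threaten the main comparison of arms.

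**What to change.** - In Section 9.4.2, delete the word significant. In Section 9.4.1, delete the sentence that gives Model 1 a selection role, and keep Model 1 for Aim 1 only.
- Write out the version of Model 2 used in Section 9.4.2 with messaging (or four-arm) main effects and their interactions with the characteristic. Without these terms, removing the filter still leaves messaging and the combined arms untestable.
- Test and report the arm interaction for all nine listed determinants whatever their Model 1 p-values. Control the false discovery rate across the set, state the level, and label the results exploratory.

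The determinants are already Model 1 predictors, so the change needs SAP wording and more interaction estimates but no new data. The real cost is the stricter per-item threshold: about 34% power instead of 66% for a 20-point interaction with 135 per cell, and about 14% instead of 39% with 67.5 per cell. Both corrected figures remain well above detection under the screen for a modifier unrelated to uptake (3.5% and about 2%). The report should still say that null interactions are weak evidence of no heterogeneity.
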